12. SAFETY

The following sections describe how the safety endpoints will be summarized.

12.1. Adverse Events

12.1.1. Definition of an Adverse Event (AE)

An AE is defined as any untoward medical occurrence in a subject or clinical investigation administered a pharmaceutical product and which does not necessarily have a causal relationship with this treatment. An AE can therefore be any unfavorable and unintended sign (including an abnormal laboratory finding), symptom, or disease temporally associated with the use of an investigational product, whether or not the event is considered causally related to the use of the product. Such an event can result from use of the product as stipulated in the protocol or labeling, as well as from accidental use or intentional misuse. Any worsening of a pre-existing condition or illness is considered an AE. Changes in vital signs are considered to be AEs only if they result in discontinuation from the study, necessitate therapeutic medical intervention, and/or if the investigator considers them to be an AE. An elective surgery/procedure scheduled to occur during a study will not be considered an AE if the surgery/procedure is being performed for a preexisting condition and the surgery/procedure has been pre-planned prior to study entry. However, if the preexisting condition deteriorates unexpectedly during the study (e.g. surgery performed earlier than planned), the deterioration of the condition for which the elective surgery/procedure is being done will be considered an AE. A treatment-emergent adverse event (TEAE) will be defined as any AE that first occurs after the first dose of study medication or any AE recorded prior to the first dose of study medication that worsens (increase in event severity) after the first dose of study medication.

12.1.2. Definition of Serious Adverse Event

An SAE is any AE occurring at any dose that meets one or more of the following definitions or outcomes:

- death
- life-threatening AE; the subject is at risk of death at the time of the event. It does not refer to an event that hypothetically might cause death if it were more severe
- in subject hospitalization or prolongation of existing hospitalization
- a persistent or significant disability/incapacity
- a medically important event that the Investigator or the sponsor judges to be serious

12.1.3. Summaries of Adverse Events

All summaries of adverse events will be based on treatment-emergent adverse events. Adverse events will be mapped to preferred terms and body systems using the Medical Dictionary for Regulatory Activities (MedDRA) coding dictionary version 19.0. The number and percentage of subjects experiencing adverse events will be summarized by system organ class (SOC) and preferred term (PT). Summaries by maximum severity and relationship to study treatment will also be provided. Serious adverse events and adverse events leading to discontinuation from the study will be presented by SOC and PT.

12.1.3.1 Overall Summary of Treatment-Emergent Adverse Events

Table 14.3.1.1 entitled *Overall Summary of Treatment-Emergent Adverse Events (Safety Population)* provides an overview of the treatment-emergent adverse event (TEAE) data. This table will include the total number of TEAE, and the number and percentage of:

- Subjects with any TEAE
- Subjects with TEAE related to study drug
- Subjects with any TEAE leading to discontinuation of the study drug
- Subjects with any serious TEAE
- Subjects with any TEAE by maximum CTCAE grade

12.1.3.2 Summary of adverse events by System Organ Class and Preferred Term

Table 14.3.1.2.1 entitled *Summary of Treatment-Emergent Adverse Events by System Organ Class and Preferred Term (Safety Population)* contains the primary presentation of the AE data. This table is prepared without regard to causality or relationship to the study drug. Subjects will be counted only once at the SOC level and will be counted once for each applicable PT; multiple occurrences of the same PT for a subject will be counted only once. The number and percentage of subjects experiencing each SOC and PT will be displayed. SOCs, and PTs within SOC, will be displayed alphabetically. The overall incidence of AEs will be summarized using counts and percentages by phase of study.

Table 14.3.1.2.2 entitled *Summary of Adverse Events that Occurred in the 4-Week Follow-up Phase by System Organ Class and Preferred Term (Safety Population)* contains a summary of only those adverse events which occurred within 4 weeks after the last dose of study medication. The number and percentage of subjects experiencing adverse events for each body system and preferred term will be displayed by phase of study.

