11. STATISTICAL CONSIDERATIONS

11.1. Sample Size

The sample size of 12 patients for this study is not based on formal statistical considerations. However, preliminary results from population PK (popPK) simulation indicate that the current study design (sample size and sparse sampling strategy) will provide adequate precision for the prediction of PK parameters (apparent clearance and volume of distribution) even considering the usual potential for subject dropouts and/or missing samples [[Wang 2012, FDA General Clinical Pharmacology Considerations for Pediatric Studies for Drugs and Biological Products 2014](#)].

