3.2. Study Design

Protocol PTC124-GD-030-DMD is a Phase 2, multiple-dose, open-label study evaluating the safety, and pharmacokinetics (PK) of ataluren in subjects aged ≥ 2 to < 5 years old with Nonsense Mutation Dystrophinopathy (nmDMD). In nmDMD, early start of treatment is important and, therefore, it is relevant to understand the correct and tolerable dose in this age group, particularly since ataluren is dosed by weight. This study is composed of 4 periods: a 4-week screening period, a 4-week study period, and a 48-week extension period for subjects who complete the 4-week study period (52 weeks total treatment), and a 4-week post-treatment follow-up period. The objective of the 48-week extension period is to assess the long-term safety of chronic administration of ataluren in this subject population.

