3.6. Study Treatments and Dose Administration

Dosing of ataluren is based on milligrams of drug per kilogram of subject body weight; body weight is re-assessed every 12 weeks. All subjects will receive approximately 10, 10, 20 mg/kg ataluren 3 times daily (TID) for 4 weeks during the PK portion and for 48 weeks during the extension period. Three doses will be administered each day; the first dose will be in the morning, the second dose will be administered in the middle of the day (midday), and the third dose will be administered in the evening.

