12.1.3.4 Summary of Adverse Events by Descending Incidence of Preferred Term

Table 14.3.1.4 entitled *Summary of Treatment-Emergent Adverse Events by Descending Incidence of Preferred Term* (Safety Population) displays the AE data by descending incidence of preferred term in the PK phase. Subjects will be counted only once for each applicable PT. The number and percentage of subjects experiencing each PT will be displayed by phase of study.

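### Most TEAE tables give only percentages of boys by phase, for phases of 4, 48 and 4 weeks and with no person-time, so for uncommon terms length alone would look like a several-fold rise in the extension

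*SAP*

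**What the plan says.** SAP 12.1.3.2 makes Table 14.3.1.2.1 the main AE presentation and sets its form: "The overall incidence of AEs will be summarized using counts and percentages by phase of study". The counting rule is that "multiple occurrences of the same PT for a subject will be counted only once". SAP 12.1.3.3 to 12.1.3.8 (Tables 14.3.1.3 to 14.3.1.8: severity, descending incidence, relationship, discontinuation, hepatic and renal toxicities, serious events) likewise give the number and percentage of subjects by phase.

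Phase of study is never defined. The SAP names a PK phase (12.1.3.4: the table "displays the AE data by descending incidence of preferred term in the PK phase") and a 4-week follow-up phase (Table 14.3.1.2.2: "only those adverse events which occurred within 4 weeks after the last dose of study medication"). The extension as the third phase follows from SAP 3.2, which describes "a 48-week extension period for subjects who complete the 4-week study period (52 weeks total treatment), and a 4-week post-treatment follow-up period", and from SAP 3.6, where dosing runs "for 4 weeks during the PK portion and for 48 weeks during the extension period".

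Treatment duration is summarised separately in Table 14.1.6 (SAP 9) and is not linked to any AE table. Neither document plans an event rate, a person-time denominator or a time-to-onset summary for AEs.

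**The concern.** Frequency and timing of TEAEs are part of the primary objective (Protocol 3.1, SAP 3.1). Protocol 11.7.1 asks for AEs to be tabulated by timing of occurrence, and the by-phase columns are the SAP's only planned tabular answer. SAP 3.2 gives long-term safety of chronic dosing as the purpose of the extension. A reader of these tables will naturally compare the PK column with the extension column. The second covers 12 times as much time (48 / 4), so its percentage would be higher even if nothing changed. The reverse holds between extension and follow-up.

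**Working it through.** **Inputs from the documents.** Phase lengths are 4, 48 and 4 weeks (SAP 3.2, 3.6); 4 + 48 = 52 weeks of treatment and 56 with follow-up, which agrees with the schedule. N = 12 (Protocol 11.1: "The sample size of 12 patients for this study is not based on formal statistical considerations"). Each boy counts once per preferred term. The plan states no AE rate or precision figure, so there is nothing of its own to reproduce.

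**Assumptions.** Constant hazard, no dropout, and a 4-week proportion p4 between 1% and 90%. Carrying the same hazard into the off-drug follow-up weeks is a further assumption.

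**Formulas.** Weekly rate r = -ln(1 - p4) / 4. Extension proportion p48 = 1 - (1 - p4)^12.

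| 4-week phase | 48-week phase | Ratio |
|---|---|---|
| 1% | 11.4% | 11.4 |
| 2% | 21.5% | 10.8 |
| 5% | 46.0% | 9.2 |
| 8.3% (1 of 12) | 64.8% | 7.8 |
| 10% | 71.8% | 7.2 |
| 25% | 96.8% | 3.9 |
| 50% | 100% | 2.0 |
| 90% | 100% | 1.1 |

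**In boys.** With p4 = 1/12, the expected counts are 1.0 boy in the PK phase and 12 x 0.648 = 7.8 in the extension. From exact binomials, treating the phases as independent, the extension count exceeds the PK count with probability 0.999.

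**Real changes are masked.** If the rate halves in the extension, the percentage still rises from 8.3% to 40.7%; the rate must fall to one twelfth for the two columns to match. In the other direction, at 0.05 events per boy-week the extension shows 1 - exp(-0.05 x 48) = 91%. Doubling the rate gives 1 - exp(-0.10 x 48) = 99%, a difference of about one boy in 12.

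**What a rate would show.** Take p4 = 1/12, so r = 0.02175 per week. Expected time at risk up to a first event is p / r per boy: 0.0833 / 0.02175 = 3.83 weeks in PK and 0.648 / 0.02175 = 29.8 weeks in the extension. For 12 boys that is 0.88 and 6.88 patient-years. The rates are 1.0 / 0.88 and 7.8 / 6.88, both 1.13 per patient-year. A constant rate then looks constant.

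**Precision.** Full person-time for 12 boys is 12 x 4 / 52 = 0.92 patient-years in PK and 12 x 48 / 52 = 11.08 in the extension. One event over 0.92 patient-years is 1.1 per year, with an exact Poisson 95% interval of about 0.03 to 6.0.

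**The case against.** The strongest reply is that the study is single-arm and descriptive, with 12 boys, stated phase lengths and no planned test or claim of rising risk. The split also has a reporting purpose: Protocol 6.2.2 and 11.3 provide for a report on the first 4 weeks, possibly separate from the extension. Listing 16.2.7.1 is sorted by subject and relative day of onset, and Table 14.1.6 gives duration. All of this stands, and it makes the point one of presentation, not an error of calculation. It does not supply a tabulated rate by phase: a listing is not a summary, and once-per-subject counts cannot be turned into rates without working through the listing.

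The size also depends on the row. Protocol 14.1.2 reports six types of TEAE in three children under 6 over two 28-day cycles. That is at least 6 events in 3 x 8 = 24 boy-weeks, or 33 with the 21-day washout: 0.25 or 0.18 per boy-week. At such rates any-AE percentages would be about 63% or 52% in 4 weeks and about 100% in 48, a ratio of 1.6 to 1.9. Three children are a thin basis, but this supports confining the large ratios to less common terms.

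Rates have limits of their own. PK-phase intervals will be too wide to show a trend for most preferred terms. A simple Poisson interval on repeat events ignores clustering within boy. SAP 15 can also impute a missing or partial onset date to Study Day 1, which puts the event in the PK phase with its small denominator.

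**Conclusion.** The concern holds as a weakness of presentation that is worth correcting. Tables 14.3.1.2.1 and 14.3.1.3 to 14.3.1.8 show percentages over phases whose lengths differ 12-fold, with no person-time. Assuming a constant rate and no dropout, preferred terms seen in 1% to 25% of boys per 4 weeks would appear about 11 to 4 times as frequent in the extension; near-universal rows would barely move. The percentages alone cannot say whether risk rises, falls or stays level with chronic dosing.

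Three stronger readings are tempting and not supported:

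- That every TEAE table has this fault. Table 14.3.1.1 has no stated phase split and also gives the total number of TEAEs, and Table 14.3.1.2.2 covers follow-up events only.
- That boys who leave early are counted as fully observed. The per-phase denominator is not stated; it could be the Safety Population or the boys entering the phase. SAP 5 says only that tables will indicate the number of subjects to which the data apply.
- That a single inflation factor applies throughout. The documents give no rate from which to derive one, and the ratio runs from 11.4 down to 1.1 over the range assumed here.

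**What to change.** - Define the phases. SAP 3.4.1 describes TEAE reporting through the extension as running to Day 392 / Week 56, which takes in the follow-up weeks, so the boundary needs stating.
- For each phase, state the number of boys entering and the patient-years observed.
- In Table 14.3.1.2.1 and the related, serious and hepatic/renal tables (14.3.1.5, 14.3.1.8, 14.3.1.7), keep the counts and percentages. Beside them add the exposure-adjusted incidence rate by phase and overall: boys with a first event in the phase per patient-year at risk, with an exact Poisson 95% interval.
- Take person-time from dosing dates in the treatment phases and from completion or withdrawal dates in follow-up.
- If total-event rates are shown, give them without a simple Poisson interval, or with one that allows for clustering within boy.
- Flag events whose onset was imputed to Study Day 1.

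The dates needed are already collected, so no new visits or data are required. The costs are some programming, extra columns, and wide intervals in the 4-week phases. It is a cheap improvement, not a free one.

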12.1.3.3 Assessment of Severity

All adverse events, both serious and non-serious, will be assessed for severity or intensity. The investigator or designee will use the following classification to rate the severity of each AE. Section 9.5 of the protocol contains the description of each of these severity grades.

- CTCAE Grade 1 Mild
- CTCAE Grade 2 Moderate
- CTCAE Grade 3 Severe
- CTCAE Grade 4 Life-threatening
- CTCAE Grade 5 Fatal

Table 14.3.1.3 entitled *Summary of Treatment-Emergent Adverse Events by System Organ Class, Preferred Term and Severity (Safety Population)* provides the presentation of adverse events with respect to the severity or intensity of the event using the scale presented above. Subjects with multiple occurrences of the same system organ class or preferred term will be summarized at the maximum severity reported for that AE. The number and percentage of subjects experiencing adverse events for each body system and preferred term will be displayed by phase of study.

12.1.3.4 Summary of Adverse Events by Descending Incidence of Preferred Term

Table 14.3.1.4 entitled *Summary of Treatment-Emergent Adverse Events by Descending Incidence of Preferred Term* (Safety Population) displays the AE data by descending incidence of preferred term in the PK phase. Subjects will be counted only once for each applicable PT. The number and percentage of subjects experiencing each PT will be displayed by phase of study.

12.1.3.5 Assessment of Relationship to Study Medication

The principal investigator must review each AE and make the determination of relationship to study drug using the following classification:

- Probable
- Possible
- Unlikely
- Unrelated

Table 14.3.1.5 entitled *Summary of Treatment-Emergent Adverse Events by System Organ Class, Preferred Term and Relationship to the Study Medication* (Safety Population) provides the presentation of adverse events by the relationship to the study drug. Subjects with multiple occurrences of the same system organ class or preferred term will be summarized using the event with the strongest relationship to study medication. The number and percentage of subjects experiencing each system organ class and preferred term will be displayed by phase of study. *Probable* and *Possible* will be group together into the *Related* category. *Unlikely* and *Unrelated* will be grouped together into the *Not Related* category.

Listing 16.2.7.1 entitled *Adverse Events* provides supportive data for Tables 14.3.1.1 through 14.3.1.5 and will be sorted by subject number and relative day of the onset of the event.

12.1.3.6 Summary of Adverse Events Leading to Discontinuation of the Study Drug

Table 14.3.1.6 entitled *Summary of Treatment-Emergent Adverse Events Leading to Discontinuation of the Study Drug by System Organ Class and Preferred Term* (Safety Population) displays all treatment-emergent adverse events resulting in an action taken of 'Discontinued'. This table will have the same structure as that of Table 14.3.1.1, however, only those treatment-emergent adverse events that led to discontinuation of study medication will be displayed. Subjects will be counted only once at the system organ class level and will be counted once for each applicable preferred term; multiple occurrences of the same preferred term for a subject will be counted only once. The number and percentage of subjects experiencing each body system and preferred term leading to discontinuation of study drug will be displayed by phase of study. These summarized results will be supported by Listing 14.3.2.2 entitled *Treatment-Emergent Adverse Events Leading to Discontinuation of the Study Drug*; this listing will be sorted by subject number and relative day of the onset of the event.

12.1.3.7 Summary of Adverse Events Associated with Specific Toxicities

This table constitutes a subset of the events reported in Table 14.3.1.1 specific to potential hepatic and renal toxicities. Subjects with hepatic or renal events will be counted only once at the system organ class level and will be counted once for each applicable preferred term; multiple occurrences of the same preferred term for a subject will be counted only once. The number and percentage of

subjects experiencing each system organ class and preferred term will be presented. All adverse events that meet this definition will be summarized in Table 14.3.1.7 entitled *Summary of Treatment-Emergent Adverse Events Associated with Specific Toxicities by System Organ Class and Preferred Term* (Safety Population) by phase of study. These summarized results will be supported by Listing 14.3.2.3 entitled *Treatment-Emergent Adverse Events Associated with Specific Toxicities*; this listing will be sorted by subject number and relative day of the onset of the event.

12.1.3.8 Summary of Serious Adverse Events

All serious adverse events will be summarized in Table 14.3.1.8 entitled *Summary of Serious Treatment-Emergent Adverse Events by System Organ Class and Preferred Term*. This table constitutes a subset of the events reported in Table 14.3.1.1. Subjects with multiple serious adverse events will be counted only once at the system organ class level and will be counted once for each applicable preferred term; multiple occurrences of the same preferred term for a subject will be counted only once. The number and percentage of subjects experiencing each system organ class and preferred term will be displayed by phase of study. These summarized results will be supported by Listing 14.3.2.1 entitled *Serious Treatment-Emergent Adverse Events*; this listing will be sorted by subject number and relative day of the onset of the event. This listing constitutes a subset of the data provided in Listing 16.2.7.1 and will contain all serious adverse events.

12.2. Clinical Laboratory Assessments

Laboratory assessments performed during each study visit and will include hematology, biochemistry and urinalysis. The presentation of laboratory results focuses on the descriptive summaries at Baseline, each scheduled follow-up evaluation, and the change from baseline. All subjects in the Safety Population who have a baseline and at least one follow-up laboratory assessment will be included in the presentation of the laboratory data. In order for a subject to be included in the analysis for a particular laboratory test, the subject must have a baseline value and a follow-up laboratory assessment for the laboratory test. Unscheduled laboratory evaluations will be presented in the listings. The summarized results will be presented for the 4 week primary PK period of the study and for the extension study data.

For each quantitative laboratory parameter, the baseline results will be summarized using descriptive statistics: n, mean, SD, median, and range. Only paired quantitative data will be summarized in the tables; all data will be presented in the listings. Results will be summarized and presented in Tables 14.3.6.1 entitled *Summary of Hematology Results by Visit* (Safety Population), 14.3.6.2 entitled *Summary of Biochemistry Results by Visit* (Safety Population), and 14.3.6.3 entitled *Summary of Urinalysis Results by Visit* (Safety Population).

Laboratory shift tables will be prepared and presented based on the normal reference ranges and presented by parameter and the scheduled observation time. Shift tables will be prepared and presented for each quantitative hematology parameter in Table 14.3.6.4 entitled *Hematology Shift Table Results by Visit* (Safety Population). Shift tables will be prepared and presented for each quantitative biochemistry parameter in Table 14.3.6.5 entitled *Biochemistry Shift Table Results by Visit* (Safety Population). Shift tables will be prepared and presented for each

quantitative urinalysis parameter in Table 14.3.6.6 entitled *Urinalysis Shift Table Results by Visit* (Safety Population).

The supportive data for Tables 14.3.6.1 through 14.3.6.6 are presented in Listing 16.2.8.4 entitled *Hematology Results*, Listing 16.2.8.5 entitled *Biochemistry Results*, and Listing 16.2.8.6 entitled *Urinalysis Results*. These listings will be sorted by subject number, parameter, and relative day.

A summary of abnormalities in laboratory variables pre-defined for safety monitoring will be summarized in Table 14.3.6.7 entitled *Summary of Abnormal Laboratory Results by Visit* (Safety Population). The supportive data for this table can be found in Listing 14.3.7.1 entitled *Abnormal Hematology Values*, Listing 14.3.7.2 entitled *Abnormal Biochemistry Values*, and Listing 14.3.7.3 entitled *Abnormal Urinalysis Values*. These listings will be sorted by subject number, parameter, and relative day.

Table 3. Safety Monitoring Parameters and Actions To Be Taken

Organ System and Laboratory Parameter	Stop Study Drug Immediately, Confirm Abnormal Value, and Then Start Work-Up	Stop Study Drug After Confirming ^a Abnormal Value, and Then Start Work-Up	Continue Study Drug, Confirm Abnormal Value, and then Start Work-Up ^a
Hepatic			
Serum total bilirubin	≥Grade 3 (≥3.0 x ULN)	Grade 2 (1.5 – 3.0 x ULN)	---
Serum GGT	≥Grade 3 (≥5.0 x ULN)	Grade 2 (>2.5 – 5.0 x ULN)	---
Serum ALT			↑ of > 150 U/L with stable or ↓ CK
Adrenal			
Plasma ACTH	---	>ULN (and plasma cortisol <LLN)	>ULN (and cortisol WNL)
Renal			
Serum cystatin C	>2.00 mg/L	>1.33 – 2.00 mg/L	---
Serum creatinine	≥ Grade 2 (≥1.5 x ULN for age)	Grade 1 (>ULN – 1.5 x ULN for age)	---
Serum BUN	≥3.0 x ULN	≥1.5 – 3.0 x ULN	---
Urine protein: urine creatinine (spot)	---	>0.40 mg:mg	---
Urine protein: urine osmolality (spot)	---	>0.30 mg/L:mOsm/kg	---
Urine blood (by dipstick)	4+ (Large)	3+ (Moderate)	2+ (Small)
Serum electrolytes			
	Grade 3-4	Grade 2	Grade 1
Serum Na ⁺ , high	>155 mmol/L	>150 – 155 mmol/L	---
Serum Na ⁺ , low	<130 mmol/L	---	---
Serum K ⁺ , high	>6.0 mmol/L	>5.5 – 6.0 mmol/L	---
Serum K ⁺ , low	<3.0 mmol/L	---	---
Serum Mg ²⁺ , high	>1.23 mmol/L	---	---
Serum Mg ²⁺ , low	<0.4 mmol/L	<0.5 – 0.4 mmol/L	---
Total serum Ca ²⁺ , high	>3.1 mmol/L	>2.9 – 3.1 mmol/L	---
Total serum Ca ²⁺ , low	<1.75 mmol/L	<2.0 – 1.75 mmol/L	---
Serum phosphorous	<0.6 mmol/L	<0.8 – 0.6 mmol/L	---
Serum HCO ₃ ⁻	<11 mmol/L	<16 – 11 mmol/L	---

^a Laboratory abnormalities may be confirmed immediately or at the next scheduled clinic visit based on investigator judgment. Abbreviations: ACTH = adrenocorticotrophic hormone, ALT = alanine aminotransferase, BUN = blood urea nitrogen, Ca²⁺ = calcium, CK = creatine kinase, GGT = gamma glutamyl transferase, HCO₃⁻ = bicarbonate, K⁺ = potassium, Mg²⁺ = magnesium, Na⁺ = sodium, ULN = upper limit of normal, WNL = within normal limits

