4.2. Inclusion Criteria

Patients must meet all of the following conditions to be eligible for enrollment into the study:

General inclusion criteria

1. Evidence of signed and dated informed consent document(s) indicating that the study candidate (and/or a parent/legal guardian) has been informed of all pertinent aspects of the study. *Note: As all study candidates are considered children under local regulation, at least one parent or legal guardian must provide written consent prior to initiation of study-related procedures, in accordance with local regulation, and the study candidate may be required to provide written assent. The rules of the responsible institutional review board/independent ethics committee (IRB/IEC) regarding whether one or both parents must provide consent and the appropriate ages for obtaining consent and assent from the patient should be followed.*
2. Males ≥ 2 to < 5 years of age
3. Body weight ≥ 12 kg
4. Willingness and ability to comply with scheduled visits, drug administration plan, study procedures, and study restrictions.
5. No clinically significant abnormality based upon laboratory assessments during the screening period, in the opinion of the Investigator; good general health, as determined during the screening period by medical history and physical examination (including vital sign measurements).

DMD inclusion criteria

6. Diagnosis of DMD based on an elevated serum CK and genotypic evidence of dystrophinopathy. *Medical documentation of phenotypic evidence of dystrophinopathy needs to be provided upon request by the PTC Therapeutics medical monitor.*
7. Documentation of the presence of a nonsense mutation in at least 1 allele of the dystrophin gene.
8. Verification that a blood sample has been drawn for sequencing of the dystrophin gene. *Note: A patient who has written documentation of a nonsense mutation as the cause of dystrophinopathy need not wait for confirmatory results to start study drug.*

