8.2.7.2. Biochemistry Laboratory Assessment

Biochemistry laboratory assessments will include sodium, potassium, chloride, bicarbonate, blood urea nitrogen, creatinine, magnesium, calcium, phosphorus, uric acid, glucose, total protein, albumin, bilirubin (total, direct, and indirect), AST, ALT, GGT, CK, lactate dehydrogenase, alkaline phosphatase, total cholesterol, high-density lipoprotein, low-density lipoprotein, triglycerides, and cystatin C. These parameters will be measured at every protocol-specified study visit. The study manual should be referenced for collection, processing, and shipping information.

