11.2. Analysis Populations

All patients who receive at least 1 dose of ataluren will be included in the analyses of safety. For each outcome measure, evaluable populations of patients will be considered to comprise all patients who have sufficient baseline and on-study measurements to provide interpretable results for the test of interest.

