11.7.2. Laboratory Parameters

Hematological and biochemistry data will be summarized by visit and will be graded according to CTCAE severity grade, when applicable. The frequencies of the worst severity grade observed will be displayed. For variables graded according to CTCAE severity grade, the frequencies of

the worst severity grade observed will be displayed. For parameters for which a CTCAE scale does not exist, the frequency of patients with values below, within, and above the normal ranges will be summarized. In the by-subject analysis, a patient having the same abnormality more than once will be counted only once based on the worst severity grade observed.

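### The normal-range shift tables cannot register a rise in CK (and probably ALT), and the SAP omits the worst-grade laboratory summary, so these enzymes lack an informative per-boy count

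*SAP*

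**What the plan says.** SAP 12.2 plans three kinds of laboratory table, backed by full listings.

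- **By-visit summaries** (Tables 14.3.6.1 to 14.3.6.3). The presentation "focuses on the descriptive summaries at Baseline, each scheduled follow-up evaluation, and the change from baseline". The statistics include the range.
- **Shift tables** (Tables 14.3.6.4 to 14.3.6.6). "Laboratory shift tables will be prepared and presented based on the normal reference ranges and presented by parameter and the scheduled observation time". They cover every quantitative parameter.
- **Pre-defined abnormalities** (Table 14.3.6.7, using the limits in SAP Table 3). Bilirubin and GGT are tiered by multiples of the upper limit of normal (ULN). ALT has one rule, a rise "of > 150 U/L with stable or ↓ CK". CK, AST and LDH have no row.

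Unscheduled results go to the listings only.

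Protocol 8.2.7.2 measures "AST, ALT, GGT, CK, lactate dehydrogenase, alkaline phosphatase" among other analytes at every visit. Protocol 4.2, criterion 6, requires: "Diagnosis of DMD based on an elevated serum CK and genotypic evidence of dystrophinopathy".

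Protocol 11.7.2 sets a different laboratory display: "Hematological and biochemistry data will be summarized by visit and will be graded according to CTCAE severity grade, when applicable". It asks for worst-grade frequencies with each patient counted once, and it keeps below/within/above-range counts for parameters that CTCAE does not grade. Neither SAP 12.2 nor the table list in SAP 14 contains a worst-grade laboratory table. SAP Table 3 carries grade labels for some analytes, but not for CK, ALT, AST or LDH.

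On who is counted, SAP 12.2 states that for each test "the subject must have a baseline value and a follow-up laboratory assessment for the laboratory test", and it leaves unpaired values to the listings. Protocol 11.2 states: "All patients who receive at least 1 dose of ataluren will be included in the analyses of safety". Its next sentence allows evaluable sets specific to each outcome measure.

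**The concern.** Laboratory abnormality is part of the first primary endpoint (Protocol 3.3), and hepatic and renal events are singled out for attention (Protocol 11.7.1, SAP 12.1.3.7). A shift table is meant to show how many boys got worse. For an analyte already above range at baseline, the top category is full from the start, so the table cannot do that.

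The gap matters more because Protocol 9.1.1 keeps laboratory abnormalities that need no intervention or further investigation out of adverse event reporting and leaves them to laboratory monitoring. For those changes the laboratory tables are the main summary.

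The pairing rule raises a smaller question. An on-treatment value beyond a fixed limit, such as serum cystatin C above 2.00 mg/L in SAP Table 3, can be read without a baseline, yet the rule as worded would leave it out of the count.

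**Working it through.** The plan gives no figure on this point, and the 12 patients are not formally derived (Protocol 11.1), so there is nothing to reproduce.

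**1. Can a normal-range shift table show a rise?**

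Let the baseline be m × ULN and the follow-up be f times the baseline. A value is High when it exceeds 1 × ULN. If m > 1 and f ≥ 1, then m × f > 1, so every rise reads High to High. The values of m and f below are assumed.

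| Baseline (× ULN) | 2-fold rise: change | 5-fold rise: change | Shift table, both rises |
|---|---|---|---|
| 1.5 | +1.5 × ULN | +6.0 × ULN | High to High |
| 3 | +3.0 × ULN | +12.0 × ULN | High to High |
| 10 | +10.0 × ULN | +40.0 × ULN | High to High |
| 50 | +50.0 × ULN | +200.0 × ULN | High to High |

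Only a fall to or below ULN registers; for example, halving 1.5 × ULN gives 0.75 × ULN, which reads High to Normal. With CK above range in all boys at baseline, 0 of 12 can shift upward.

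**2. Which analytes are affected?**

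- CK: elevation is an entry requirement. It is part of the diagnosis, so I assume that it persists to the baseline sample.
- ALT: inferred. SAP Table 3 judges ALT by an increment read against CK, where bilirubin and GGT are judged by multiples of ULN. That choice makes sense if ALT is expected to be raised by muscle damage.
- AST and LDH: assumed. The documents do not give their level at entry.

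**3. What other per-boy categorical summary exists?**

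| Enzyme | SAP Table 3 row | Worst-grade table in SAP |
|---|---|---|
| CK | none | none |
| AST | none | none |
| LDH | none | none |
| ALT | one threshold, conditional on CK | none |

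**4. What can the by-visit change show?**

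Suppose that one boy's ALT goes from 300 to 900 U/L (assumed) and the other 11 are unchanged. The mean change is (900 − 300)/12 = 50 U/L, and the maximum change is +600 U/L. The range exposes the outlier. It does not count affected boys, and it does not set ALT beside that boy's CK, GGT and bilirubin.

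**5. How often would pairing exclude a boy?**

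SAP 5 defines baseline as the last value before first dose, and laboratory tests are drawn at both Screening and Day 1. A boy lacks a baseline only if both are unusable. With per-sample loss p (assumed, independent between the two visits), the chance per boy is p², the expected number is 12p², and the chance of at least one is 1 − (1 − p²)^12.

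| p | p² | Expected of 12 | At least one of 12 |
|---|---|---|---|
| 5% | 0.0025 | 0.03 | 3.0% |
| 10% | 0.01 | 0.12 | 11.4% |
| 20% | 0.04 | 0.48 | 38.7% |

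Each boy lost is 1/12 = 8.3% of the sample.

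**The case against.** The strongest reply is that the shift table is one output of several, and that with 12 boys the by-visit ranges and complete listings already expose individual rises. This largely stands, and it limits the point. Four stronger readings are tempting, and the documents do not support them.

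- **That worsening cannot show anywhere.** Change from baseline with its range, the ALT rule and the listings can all show it. In the example above, a rise of 600 U/L also meets the ALT rule, provided that CK is stable or falling.
- **That the shift tables cannot signal liver harm.** They also cover GGT, alkaline phosphatase and bilirubin, which nothing in the documents says are raised at entry. GGT and bilirubin have tiers in SAP Table 3, and hepatic adverse events have their own table.
- **That worst CTCAE grades would hit the same ceiling.** The documents give no CTCAE limits for these enzymes, so this cannot be checked. A scale with several grades is not the same as a single High category.
- **That unpaired boys vanish, in contradiction of Protocol 11.2.** Exclusion is test by test and from summary tables only, and the listings keep the values. Laboratory findings reported as adverse events enter tables with no baseline requirement. Protocol 11.2 itself allows outcome-specific evaluable sets, and a shift or change needs a baseline by definition. Counting Day 1 alone as baseline would give 46.0%, 71.8% and 93.1% in place of the last column in step 5, but SAP 5 lets the screening value stand in. Criterion 5 also calls for screening laboratory results, and SAP 5 expects little missing data.

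The reply does not reach the missing worst-grade table, the absence of CK, AST and LDH from Table 3, or the confinement of unscheduled values to listings.

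**Conclusion.** The point holds in a limited form and is worth correcting. Given CK above range at baseline, the CK shift table cannot register worsening in any of the 12 boys. The same is likely for ALT and is assumed for AST and LDH. Because the SAP also leaves out the worst-grade display in Protocol 11.7.2, CK, AST and LDH have no informative per-boy categorical summary, and ALT has only one threshold conditional on CK. The weakness lies in counting and presentation. The data are collected and listed, and a large rise in one boy can be seen in the by-visit range.

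The pairing rule is a secondary matter. It needlessly removes threshold abnormalities that require no baseline, but under the stated assumptions it would affect fewer than one boy in expectation (0.03 to 0.48 of 12).

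**What to change.** 1. Restore the worst-CTCAE-grade laboratory tables of Protocol 11.7.2, one count per boy, with normal-range counts where no CTCAE scale exists.
2. Add one table for CK, ALT, AST and LDH giving each boy's worst post-baseline ratio to his own baseline, including unscheduled values. Bands such as ≤1.5, >1.5–2, >2–3 and >3 would serve; they are a proposal and do not come from the documents. Show ALT and AST beside CK, GGT and bilirubin from the same visit. This table does not depend on where the CTCAE limits fall.
3. Limit the pairing rule to change-from-baseline and shift columns. Count post-baseline abnormalities in every treated boy with any post-baseline value, with a row for missing baseline.

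The normal-range shift tables can stay for the other analytes. The cost is SAP wording and a small amount of extra programming. No new samples are needed, and no clinical rule changes.
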